## **Study rationale**

Robotics has entered the mainstream of cardiac surgery, with large numbers of cases now performed at specialized centers. But despite the demonstrated benefits and increasing number of robotic cases, there has been slow adoption of this technology partly due to lack of proper training. An important aspect of modern surgical education is that it utilizes competency-based training instead of time-based training or numbers of performed procedures. The classic stepwise educational approach in robotic cardiac surgery involves increasing entrustment with increasing levels of surgical skills. Until now, this approach has relied on clinical training with little use of simulation-based training as initial part of the entrustment process. Simulation-based training allows for skill development outside of the operating room in a controlled and safe environment with no patient risk and ample opportunities for feedback and correction of errors.

A recent study compared currently available simulation modalities used in cardiac robotic surgical training (wet lab, dry lab and virtual reality) and indicated that trainees had the greatest skill improvement in the wet lab. However, the study was not designed to examine validity evidence of the wet lab model and had a small number of participants (n=10) in the wet lab group.

The skills and performance levels of trainees need to be objectively assessed to ensure the surgeons competency level before they operate on real patients. Before using simulation-based training to assess competency it is imperative that the assessment tool is examined to ensure it is supported by validity evidence. Currently, it is unclear how much wet lab robotic cardiac surgery simulation training is needed before a trainee can proceed to real operations and there is a need for identifying a relevant pass/fail level to ensure competency before operating on patients.

Learning curves are increasingly used in the assessment of competency and training program design. Methods currently used to analyze learning curves in surgery are mainly descriptive and need to be rigorous with quantifiable parameters to allow future surgeons to benefit from established performance standards. Data on learning curves in robotic cardiac procedures in a real-world setting exists, but little is known about learning curves in a wet lab simulation setting. Learning curves can support a competence-based approach to assessment for learning. It has been claimed that surgeon expertise in performing both routine and high-risk cardiac procedures before proceeding to robotic-assisted surgery is essential. However, it is possible that as robotic simulators evolve, the non-robotic experience gap may be substantially reduced. By contrast, according to the expertise reversal effect, an instructional design that is beneficial to a novice learner may be detrimental to a more experienced learner and vice versa. The skills acquisition rate of robotic novices with expertise in cardiac surgery may be faster than robotic novices with limited cardiac surgery experience, which may suggest that robotic skills training should only be commenced after the surgeons master the non-robotic techniques. However, if this is not the case, robotic skills training programs should be implemented early in cardiac surgeons' careers to allow them to develop expert-level skills as early in their careers as possible.

The current study will be the first to examine validity evidence for the wet lab robotic cardiac surgery model with the largest number of participants to-date and will be the first to analyze learning curves in wet lab simulation settings for subjects with different surgical background. Results of the study could help in establishing standardized training pathways in robotic cardiac surgery as recommended at the ORSI Consensus Meeting on European Robotic Training (OCERT) and facilitate faster spread of robotic cardiac surgery. Most importantly, establishing valid assessment methods will allow us to ensure that robotic surgeons are trained

until proficiency in the wet lab before operating being allowed to progress on real patients. This will ensure that all patients are certain to receive expert-level care regardless of where and by whom, they are treated.

## **Objectives**

*Primary:*

- to investigate validity evidence for simulation-based assessment using the wet lab robotic cardiac surgery model.

*Secondary:*

- to analyze performance curves in the wet lab for a robotic cardiac surgery model.
- to assess rate of skills acquisition of cardiac robotic skills in cardiac surgery trainees versus non-cardiac surgery trainees.

## **Materials and methods**

We aim to assess the validity evidence for the wet lab robotic cardiac surgery simulation model using the contemporary framework for validity proposed by Messick, which includes five sources of validity evidence: content evidence, response process, relations to other variables, internal structure, and consequences.

We will test the validity evidence for the three wet lab tasks used in robotic cardiac surgery using three groups of participants: experienced robotic cardiac surgeons (5), robotic cardiac surgery novices (8) and robotic non-cardiac surgery novices (8).

Wet lab simulator: tasks will be performed in porcine models with the da Vinci Xi Surgical System (Intuitive Surgical, California, USA).

### 1. Content evidence:

Three wet lab tasks, which all are parts of real robotic cardiac operations have been chosen by surveying experienced robotic cardiac surgeons participating in the study:

- robotic harvesting of 10 cm internal thoracic artery (ITA) from the porcine chest wall
- robotic-assisted placement of 5 sutures in the mitral annulus of the porcine heart (one on each trigone and three consecutive annular sutures)
- robotic-assisted closure of the porcine atrium

### 2. Response process:

All participants will receive a short oral introduction to the da Vinci Xi Surgical System and will be shown videos of robotically assisted cardiac procedures highlighting basic operative techniques and relevant anatomy. They will then complete the three previously selected tasks to familiarize themselves with the wet lab simulator. Finally, they will complete all 3 tasks again and this will be used to assess their base-line performance.

Next, five experienced robotic cardiac surgeons from different international sites will perform each task 4 times more. Subjects in the cardiac and non-cardiac groups will perform the tasks until mastery is achieved based on the performance of the expert robotic surgeons. To ensure

the successful completion of the task, each participant will be required to pass each exercise 2 consecutive times with the only one failure between the attempts allowed.

The mastery learning level for the tasks will be calculated from the mean time-based score (TBS) of the experienced surgeons 2 last attempts for each task.

Time-based scoring equation will be calculated as follows (adapted from Valdis et al):

$$\text{Score} = \text{Max time} - \text{Completion time} - \text{Errors}$$

-Max time is the total time that an individual will be allowed to complete the task during the base-line performance.

-Completion time is either;

- 1) The mean time for completion of each expert's last 2 attempts which will be used to calculate the mastery learning level based on the formula above
- 2) The time taken by each study participant to complete the task

- Errors will be divided in minor and major ones. A minor error will result in adding a 10 second penalty time to the TBS equation. A major error will result in a score of zero, regardless of time to completion.

Minor errors:

- 1) moving robotic arms out of view
- 2) robotic arm collision
- 3) drop of the needle

Major errors:

- 1) avulsion of ITA or suturing model
- 2) tearing/ fraying the suture
- 3) gross tissue damage (specifically with the cautery)

All tasks will be recorded on the robot's camera and evaluated blinded using the modified Global Evaluative Assessment of Robotic Skills (mGEARS) score (Appendix 1) by two not participating surgeons with experience in robotic cardiac surgery from two different sites in Europe and North America. In modified GEARS score the tasks will not be rated on autonomy domain as autonomy cannot be evaluated from recordings.

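### As written, an expert's major error enters the mastery level as a zero and eases the bar novices must reach on that task; the mean-time wording would give a different level

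*Combined protocol and SAP*

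**What the plan says.** All of this is in section 2 (Response process) of the combined protocol and SAP unless noted.

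- **Level as a mean of scores:** "The mastery learning level for the tasks will be calculated from the mean time-based score (TBS) of the experienced surgeons 2 last attempts", separately for each task.
- **Level from a mean time:** under the definition of completion time, "The mean time for completion of each expert's last 2 attempts which will be used to calculate the mastery learning level", with the score formula then applied.
- **Score:** Max time, less completion time, less errors. For minor errors, "A minor error will result in adding a 10 second penalty time to the TBS equation". For major errors, "A major error will result in a score of zero, regardless of time to completion".
- **Data behind the level:** after familiarization and base-line, "five experienced robotic cardiac surgeons from different international sites will perform each task 4 times more". The last two count.
- **Use of the level:** "Subjects in the cardiac and non-cardiac groups will perform the tasks until mastery is achieved based on the performance of the expert robotic surgeons".

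The plan does not say what happens to an expert attempt with a major error when the level is set, or how errors enter when a mean time is used. Section 5 (Consequences) adds a pass/fail level for mastery learning by the contrasting groups method, also using the experts' last two attempts. It does not say how that level relates to the one in section 2.

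**The concern.** The zero rule is there to fail an unsafe attempt. In a novice's score it does that. In the calculation of the standard it works the other way: a zero in the experts' mean lowers the mean, so an expert's avulsed artery or torn suture makes the task easier for novices to pass. The second description of the level does not settle the matter. Two analysts following section 2 could set different levels from the same recordings once an expert has made a major error.

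The level decides when each of the 16 novices stops training on the task. It therefore feeds training time to mastery (Secondary outcome measures) and the length of the performance curve for that task. The study rationale gives training to proficiency before operating on patients as the purpose, and a bar lowered by a failed expert attempt works against it.

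**Working it through.** The plan states no mastery level, Max time, expert time or expert error rate, so there is no figure of its own to reproduce. The check is arithmetic on the score formula.

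**Inputs.** From section 2: 5 experts × 2 last attempts = 10 attempts per task; a major error scores 0; each minor error costs 10 s. Assumed: expert completion time T = 600 s; Max time M = 900, 1200 or 1800 s; expert major-error rate q = 1% or 2% per attempt.

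**Step 1: no major error.** The score is linear in time and penalties. The mean of the scores therefore equals M − mean time − mean penalty, and the two descriptions give one level. A simulated check with M = 1800 s gave 1175.8 by both. If the mean-time route summed an expert's penalties over the two attempts instead of averaging them, it gave 1155.8, so the error term also needs stating.

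**Step 2: one major error among the 10, other attempts equal and free of minor errors.**

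- Mean of scores: 9 × (M − T)/10 = 0.9 (M − T), a 10% drop.
- Mean time, zero rule not applied: M − T, no drop.
- Mean time, one score per expert, that expert's score set to zero: 4 × (M − T)/5 = 0.8 (M − T), a 20% drop.

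**Step 3: in seconds.** An error-free novice passes at a completion time of M − level. This is T + 0.1 (M − T) for the mean of scores and T + 0.2 (M − T) for the zeroed expert.

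| Assumed M (s) | Level, no major error | Level, mean of scores | Passing time (s) | Level, one expert zeroed | Passing time (s) |
|---|---|---|---|---|---|
| 900 | 300 | 270 | 630 | 240 | 660 |
| 1200 | 600 | 540 | 660 | 480 | 720 |
| 1800 | 1200 | 1080 | 720 | 960 | 840 |

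Under the mean of scores, the passing time relaxes by 30, 60 or 120 s, which is 5%, 10% or 20% of 600 s. One minor error costs 10 s.

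**Step 4: how often, and on average.** With independent attempts, the chance that at least one of the 10 has a major error is 1 − (1 − q)^10, which is 9.6% at q = 1% and 18.3% at q = 2%. The expected relaxation under the mean of scores is q (M − T): 3, 6 or 12 s at 1%, and 6, 12 or 24 s at 2%.

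**The case against.** The strongest reply is that section 2 contains one equation. The first sentence names the quantity, and the completion-time entry says which time goes into it. Much of this stands: the descriptions agree whenever experts make no major error and minor penalties are averaged. A reader might infer that the plan contradicts itself in every case, and the text does not support that. What remains is that the headline definition, followed literally, lets a failed expert attempt lower the bar.

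A reader might also infer more about size and reach than the documents allow:

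- **Frequency.** An assumed 5% error rate would give a 40% chance of an effect on a given task and 79% on at least one of three. Nothing in the plan supports that rate for surgeons with more than 50 robotic cardiac operations, on their fifth and sixth attempts at the task. The three-task figure also assumes independence within a surgeon.
- **A level of zero.** The mean-time entry refers to each expert, so the natural reading zeroes one score in five and does not collapse the whole level.
- **Reach.** An error on one task moves that task's level only. Both novice groups face the same bar, so it does not by itself favour either. The base-line comparison in section 3 (Relations to other variables) does not use the level. A novice's own major error still scores zero.

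Finally, counting failed expert attempts can be defended as showing what experts achieve under the scoring novices face. That is a fair reason to report the level with zeros included. It does not make it a good stopping standard, because it rewards novices for an expert's failure.

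**Conclusion.** The point holds as a conditional one. If an expert makes a major error in either of the last two attempts at a task, and that attempt would otherwise have scored above zero, the mean-score rule lowers that task's level. For one error with other attempts equal, the drop is 10% of (Max time − expert time). The mean-time wording gives no drop or 20%, and no section of the plan chooses between them.

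On the assumed times, one such error relaxes the passing time by 30 to 120 s. Averaged over an assumed 1–2% error rate, the relaxation is 3 to 24 s. The figures in seconds rest wholly on those assumptions; the 10% and 20% follow from the plan's own counts. The consequence falls on training time to mastery for the affected task. It should be corrected before novices train, because a stated rule moves the standard in the wrong direction and the remedy is cheap.

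**What to change.** Before novices start training, replace the two descriptions in section 2 with one:

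'For each task the mastery level is Max time minus the mean completion time minus the mean minor-error penalty (10 s each) over the experienced surgeons' last two attempts, excluding any attempt with a major error.'

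Also:

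- report, by task, the number of expert attempts excluded;
- show the level with zeros included as a sensitivity figure;
- state how this level relates to the contrasting-groups pass/fail level in section 5, and which of the two decides when a novice stops.

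Exclusion is preferable to substituting an earlier attempt by the same surgeon. Earlier attempts, base-line included, may be slower, and substituting one could itself lower the bar.

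The cost is a few sentences and no new data. If an expert errs, the level rests on slightly fewer than 10 attempts and is conditional on successful ones. It is then slightly stricter than the mean with zeros, so novices may need a little more training.

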### 3. Relations to other variables:

We will analyze variation in performance scores (TBS and mGEARS) between experienced robotic cardiac surgeons and robotic novices during their base-line performance. We will use TBS score for the assessment of novice performance during the subsequent training rounds.

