## 5. Consequences:

To investigate the consequence of testing we will define a pass/fail level to be used for mastery learning. The pass/fail level will be determined using the “contrasting groups method” for the mean TBS and mGEARS score for the last two attempts in the experienced group.

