#### *Exclusion criteria*

- Novices with > 5 hours experience of any robotic system.

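### The time-based score has no lower bound, so an attempt without a major error scores below a major error whenever completion time plus minor-error penalties exceeds Max time

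*Combined protocol and SAP*

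**What the plan says.** Section 2, Response process, defines TBS as Max time minus completion time minus errors. Three rules go with it:

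- Minor errors: "A minor error will result in adding a 10 second penalty time to the TBS equation". Their number is not capped.
- Major errors (avulsion, suture damage, gross tissue damage): "A major error will result in a score of zero, regardless of time to completion".
- Time limit: "Max time is the total time that an individual will be allowed to complete the task during the base-line performance". No value is given for any task, and no score is stated for an attempt unfinished at the limit.

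No section sets a minimum score. TBS for each task is the only primary outcome listed under Outcomes. Its use continues after base-line; section 3, Relations to other variables, says "We will use TBS score for the assessment of novice performance during the subsequent training rounds". The secondary objectives are "to analyze performance curves in the wet lab for a robotic cardiac surgery model" and "to assess rate of skills acquisition of cardiac robotic skills in cardiac surgery trainees versus non-cardiac surgery trainees". The Statistical plan uses Kruskal-Wallis for novices against experts at base-line and Mann-Whitney for continuous variables.

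**The concern.** The split into minor and major errors, with a major error cancelling all credit for speed, implies that zero is meant as the worst result. As written it is not. Penalties come off after the completion time, so a late finish with a few needle drops or arm collisions goes negative while an avulsion stays at zero.

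The planned group tests use ranks, so the order of scores is what counts. Late finishes are most plausible among novices. The exclusion criterion is "Novices with > 5 hours experience of any robotic system", and participants have one familiarisation round before base-line. At stake is whether TBS orders novice attempts as intended, both in the performance curves and in any comparison of cardiac with non-cardiac novices.

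**Working it through.** **Inputs from section 2.** M = Max time (no value given), t = completion time, k = number of minor errors, 10 s per minor error, major error = 0.

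**Condition.** Without a major error, TBS = M − t − 10k. This is below zero when t + 10k > M, and equals zero when t = M and k = 0. Writing s = M − t for the time left, the fewest minor errors that give a negative score are:

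| Time left s | Minor errors k | Score s − 10k |
|---|---|---|
| 0 s | 1 | −10 |
| 10 s | 2 | −10 |
| 30 s | 4 | −10 |
| 60 s | 7 | −10 |
| 120 s | 13 | −10 |

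These thresholds do not depend on M. They apply even if the limit is strictly enforced.

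**Frequency (assumed inputs).** The plan has no figure to reproduce. Assume t is normal with SD 0.2M, k is Poisson with mean 2, and M is 600 to 1800 s. The share of attempts without a major error that finish within the limit and score below zero is the sum over k of P(k) × P(M − 10k < t ≤ M):

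| Mean of t | M = 1800 s | M = 600 s |
|---|---|---|
| 60% of M | 0.3% | 1.2% |
| 75% of M | 1.1% | 3.5% |
| 90% of M | 2.0% | 6.2% |

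Timed-out attempts are left out because the plan gives no score for them.

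**Effect by analysis.**

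- *Performance curves.* These use TBS values from successive sessions. A change from a negative score to a major error is recorded as a gain.
- *Novice groups, 8 v 8, if TBS is compared.* With m major errors in one group and n negative scores in the other, ranking major errors last instead of at zero changes the Mann-Whitney U by m × n out of 8 × 8 = 64 pairs. One and one gives 1/64 = 1.6 points of probability of superiority; two and two gives 4/64 = 6.3 points. The expected net shift is zero if both groups have the same rates.
- *Base-line, 5 experts v 16 novices pooled.* Reordering among novices changes no expert-novice pair, so the test is unchanged unless an expert makes a major error (taking it that no expert is slow enough to score below zero).
- *Pass/fail and training time to mastery.* With a mastery level above zero, a zero and a negative score both fail, so neither changes.
- *Cronbach's alpha.* In assumed cases (3 tasks, 16 novices, M = 1200 s, major-error rate 5% to 25%) scoring as written and scoring with a floor differ by at most 0.02.

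**The case against.** The algebra is not in dispute; the reach is.

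- *Slow attempts in general.* A reader might infer that any slow attempt with minor errors ranks below an avulsion. It does not: t + 10k must exceed M. With 30 s left, three minor errors give exactly zero and a fourth is needed to go below.
- *The main analyses.* The pooled base-line test, pass/fail decisions and alpha are unaffected or barely affected. The Outcomes section gives training time to mastery as a secondary outcome; this fits the skill-acquisition objective and is also unaffected. An 8 v 8 rank test of TBS is not named in the plan; it is inferred from the general Mann-Whitney sentence. All of this stands.
- *A reversed conclusion.* With three major errors in one novice group, three negative scores in the other and the remaining scores interleaved, U moves from 25/64 = 0.39 (major errors last) to 34/64 = 0.53 (as written). That reverses the direction, but the case is constructed. Even at the 6.2% rate, three or more negatives among eight has a probability of about 1%, and neither result is significant (p = 0.49 and 0.87).
- *A large false gain on the curve.* A training attempt 60 s over the limit with three minor errors would score −60 − 30 = −90, so an avulsion in the next session would show as a gain of 90. No section says training attempts may overrun.
- *Time-outs.* If unfinished attempts were entered at Max time, those with at least one minor error would add 2.0%, 9.1% or 26.7% for the three assumed means. That scoring rule is not in the plan.
- *Safety is rated elsewhere.* The mGEARS force-sensitivity item covers tissue tears and suture breakage, so an avulsion need not go unseen. But mGEARS is secondary, and TBS is the score named for novice performance in training rounds.

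These points limit the consequence. They do not restore the intended order, and no section supplies a floor.

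**Conclusion.** The concern holds in conditional form. The stated rule mis-orders attempts on the only primary outcome whenever t + 10k > M, whatever Max time is, and an error-free finish exactly at the limit ties with a major error. The size is uncertain: about 0.3% to 6% of attempts, counting only those finished within the limit, and resting wholly on the assumed times and error rates. The exposed analyses are the TBS performance curves, any TBS comparison of the two novice groups, and the base-line test if an expert makes a major error. The documents do not support saying that the primary comparison is invalid or that a conclusion is likely to reverse. The correction should still be made before data are seen, because with eight per group a scoring rule chosen afterwards could be questioned.

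**What to change.** In section 2, Response process, state that:

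1. A major error is the worst possible result. In rank tests it is ranked below every attempt without one.
2. In curves and other value-based analyses, a major error stays at 0, attempts without one are floored just above it (for example at 1), and the number of major errors is reported separately.
3. An attempt unfinished at the limit has a defined score, and the same Max time applies in every session.

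A floor at 0 would not be enough: scores of −10 to −40 would all become 0 and tie with an avulsion.

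The cost is three or four sentences and no new data. The downside is that slow attempts with minor errors tie at the floor in value-based analyses, only just above a major error, which is why major errors need their own count.

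A separate clarification, not part of this point, is how an expert's major error enters the mastery level and the pass/fail level based on the "mean TBS and mGEARS score for the last two attempts in the experienced group". One zero among 5 × 2 = 10 otherwise equal attempts lowers the mean TBS by 10%.
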